## 6.3 SUMMARIES OF CONDUCT OF STUDY

Enrollment, major protocol violations, and discontinuations from the study will be listed. The incidence of treatment discontinuation for reasons other than disease progression will be tabulated.

Data related to administration of study treatment components will be listed, and any dose modifications will be flagged. The number of doses, treatment cycles, average dose received, and relative dose intensity for each treatment component will be summarized using descriptive statistics (mean, standard deviation, median, and range).

## 6.4 SUMMARIES OF DEMOGRAPHIC AND BASELINE CHARACTERISTICS

Demographic and baseline characteristics, such as age, sex, race, and duration of malignancy, will be summarized using descriptive statistics (mean, standard deviation, median, and range) for continuous variables and frequencies and percentages for categorical variables.

## 6.5 SAFETY ANALYSES

The safety analyses will include all treated patients (i.e., patients who received any amount of study treatment). Data for patients in the dose-escalation phase will be summarized by cohort *and histology type*, and data for patients in the expansion phase will be summarized by histologic subtype (FL or DLBCL).

Safety will be assessed through summaries of adverse events and changes from baseline in laboratory test results, shift-tables of ECGs findings, and vital signs.

All adverse events occurring on or after first study treatment will be summarized by mapped term, appropriate thesaurus levels, and NCI CTCAE, Version 4.0 grade. All serious adverse events, adverse events of special interest, and selected adverse events will be summarized and listed.

Deaths reported during the treatment period and during post-treatment follow-up will be listed *and summarized*.

Relevant laboratory *results* will be displayed by time, with Grade 3 and 4 values identified as appropriate.

## 6.6 EFFICACY ANALYSES

The primary and secondary efficacy analyses will include *the primary efficacy population and the intent-to-treat population for patients enrolled in the expansion phase, with patients grouped according to histologic subtype, and will be performed by treatment group. In addition, patients with FL and DLBCL who received polatuzumab vedotin and lenalidomide at the RP2D during the dose-escalation phases will be pooled for analysis by histology with patients treated in the expansion phase at the same dose levels.*

Response will be determined on the basis of PET-CT scans or CT scans alone, using the Lugano 2014 criteria (see [Appendix 5](#)).

### 6.6.1 Primary Efficacy Endpoint

The primary efficacy analysis will be estimation of the proportion of patients achieving a CR at EOI, as determined by the IRC through use of the PET-CT–based Lugano 2014 criteria. Point estimates will be presented, along with the corresponding two-sided 90% Clopper-Pearson exact CIs. Patients without a post-baseline tumor assessment will be considered non-responders.

### 6.6.2 Secondary Efficacy Endpoints

The secondary efficacy analyses will be estimation of the proportion of patients achieving each of the following endpoints:

- CR at EOI, as determined by the investigator on the basis of PET-CT scans

- CR at EOI, as determined by the *IRC and* investigator on the basis of CT scans alone
- Objective response (defined as a CR or PR) at EOI, as determined by the IRC and by the investigator on the basis of PET-CT scans
- Objective response (defined as a CR or PR) at EOI, as determined by the IRC and by the investigator on the basis of CT scans alone
- Best response of CR or PR during the study, as determined by the investigator on the basis of CT scans alone

Point estimates will be presented, along with the corresponding two-sided 90% Clopper-Pearson exact CIs. Patients without a post-baseline tumor assessment will be considered non-responders.

### **6.6.3 Exploratory Efficacy Endpoints**

Exploratory efficacy analyses will include estimation of the proportion of patients achieving each of the following endpoints:

- For patients who have positive PET scans at EOI:
  - CR at 12 months, as determined by the IRC and by the investigator on the basis of PET-CT scans, *in FL patients*
  - *CR at EOC, as determined by the IRC and by the investigator on the basis of PET-CT scans, in DLBCL patients*

Point estimates will be presented, along with the corresponding two-sided 90% Clopper-Pearson exact CIs. Patients without a post-baseline tumor assessment will be considered non-responders.

Exploratory efficacy analyses will also be performed on the following endpoints:

- PFS
- EFS
- DFS
- OS

PFS, EFS, DFS, and OS will be summarized descriptively using the Kaplan-Meier method ([Kaplan and Meier 1958](#)). For the PFS, EFS, and DFS analyses, data for patients without an event of interest will be censored at the date of the last tumor assessment. For patients without post-baseline tumor assessments, data will be censored at the date of initiation of study treatment plus 1. For the OS analysis, data for patients who have not died will be censored at the date the patient was last known to be alive. Where medians are reached, the corresponding estimated median will be provided, along with the 95% CI estimated using the method of [Brookmeyer and Crowley \(1982\)](#). In addition, landmark estimates of the proportion of patients who are

event free at 6 months, 9 months, 1 year, and 2 years will be provided, along with 95% asymptotic CIs using Greenwood's formula for standard errors.

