#### Exploratory Efficacy Objective

The exploratory efficacy objective for this study is to evaluate the long-term efficacy of G+Pola+Len and R +Pola +Len on the basis of the following endpoints:

- For patients who have positive PET scans at EOI: CR at 12 months, as determined by the IRC and by the investigator on the basis of PET-CT scans *in FL patients*; CR at end of consolidation (EOC), as determined by the IRC and by the investigator on the basis of PET-CT scans, *in DLBCL patients*
- PFS, defined as the time from initiation of study treatment to first occurrence of disease progression or relapse, as determined by investigator on the basis of CT scans alone, or death from any cause
- EFS, defined as the time from initiation of study treatment to any treatment failure, including disease progression or relapse, as determined by investigator on the basis of CT scans alone, initiation of new anti-lymphoma therapy, or death from any cause, whichever occurs first
- Disease-free survival, defined, among patients achieving a CR, as the time from the first occurrence of a documented CR to relapse, as determined by the investigator on the basis of CT scans alone, or death from any cause, whichever occurs first
- Overall survival, defined as the time from initiation of study treatment to death from any cause

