### 2.2.3 Exploratory Efficacy Objective

The exploratory efficacy objective for this study is to evaluate the long-term efficacy of G+Pola+Len *and R +Pola +Len* on the basis of the following endpoints:

- For patients who have positive PET scans at EOI:
  - CR at 12 months, as determined by the IRC and by the investigator on the basis of PET-CT scans *in FL patients*
  - CR at end of consolidation (EOC), as determined by the IRC and by the investigator on the basis of PET-CT scans, *in DLBCL patients*
- PFS, defined as the time from initiation of study treatment to first occurrence of disease progression or relapse, as determined by investigator, or death from any cause

- EFS, defined as the time from initiation of study treatment to any treatment failure, including disease progression or relapse, as determined by investigator, initiation of new anti-lymphoma therapy, or death from any cause, whichever occurs first
- Disease-free survival (DFS), defined, among patients achieving a CR, as the time from the first occurrence of a documented CR to relapse, as determined by the investigator, or death from any cause, whichever occurs first
- Overall survival (OS), defined as the time from initiation of study treatment to death from any cause

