#### **4.3.2 Dosage, Administration, and Compliance**

Patients enrolled in the dose-escalation phase or the expansion phase will receive six 28-day cycles of induction treatment with obinutuzumab *or rituximab*, polatuzumab vedotin, and lenalidomide. When study treatments are given on the same day, they will be administered sequentially in the following order: lenalidomide, *obinutuzumab or rituximab*, and polatuzumab vedotin.

Patients with DLBCL who achieve a CR or PR at EOI will receive post-induction treatment (referred to as consolidation) with lenalidomide and *rituximab*, and patients with FL who achieve a CR, PR, or SD at EOI will receive post-induction treatment (referred to as maintenance) with lenalidomide and obinutuzumab. When study treatments are given on the same day, lenalidomide will be administered prior to obinutuzumab *or rituximab*.

Post-induction treatment should start 8 weeks ( $\pm 1$  week) after Day 1 of the final cycle of induction and will continue until disease progression or unacceptable toxicity for up to 2 years for maintenance treatment or *6 months* for consolidation treatment.

Treatment regimens are summarized in [Table 1](#), [Table 2](#), [Table 4](#), and [Table 5](#) for R/R FL patients and [Table 6](#), [Table 7](#), [Table 9](#), and [Table 10](#) for R/R DLBCL patients (see Section 3.1) and depicted in [Figure 4](#). All eligible patients in both dose-escalation and expansion phases should receive induction and post-induction (if indicated) therapy.

Premedication and treatment for TE prophylaxis should be administered as described in Section [4.3.2.5](#).

Any overdose or incorrect administration of any of the study treatments should be noted on the Study Drug Administration electronic Case Report Form (eCRF). Adverse events associated with an overdose or incorrect administration of any of the study treatments should be recorded on the Adverse Event eCRF.

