### Schedule of Assessments for Patients with Follicular Lymphoma (cont.)

---

- informed consent and within the defined window may be used as screening and baseline assessments; such tests do not need to be repeated for screening purposes.
- b Patients who complete maintenance treatment or discontinue maintenance treatment prematurely will undergo assessments at EOM.
  - c EOI assessments should be performed 6–8 weeks after Day 1 of the last induction cycle. As an exception, patients who discontinue induction treatment prematurely because of an adverse event may undergo EOI assessments 4–8 weeks after their last dose of study treatment.
  - d Patients who complete treatment or discontinue treatment for reasons other than disease progression will undergo assessments every 3 months during the post-treatment FU period, which will continue until disease progression, the start of new anti-lymphoma treatment, or the end of the study, whichever occurs first. The first post-treatment FU visit is 3 months after the EOI visit for patients who do not receive maintenance treatment and 3 months after the last dose for patients who receive maintenance treatment. Patients who experience disease progression will undergo limited assessments every 3 months during the survival FU period, which will continue until the end of the study. The end of the study is defined as the time when all enrolled patients have completed or discontinued study treatment or when the Sponsor ends the study.
  - e Informed consent must be documented before any study-specific screening procedure is performed.

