## Appendix 2 Schedule of Assessments for Patients with Diffuse Large B-Cell Lymphoma (cont.)

	Screening a		Induction (6-months; 28-day cycles)								EOI	Consolidation (6 months)		EOC b	Post- Treatment FU Period (Q3M) d	Survival FU Period (Q3M) d
	D -28 to D -1	D -14 to D -1	Cycle 1 (± 1 d)				Cycles 2-6 (± 2 d)				After Last Induction Dose c	Monthly (± 3 days)	Every 2 months (± 1 wk)	35 Days after Last Dose		
			D1	D8	D15	D22	D1	D8	D15	D22						
Plasma for cytokine analysis			x m					x m, n								
Optional peripheral blood sample for RCR v			x m													
Tumor tissue specimen	x w												(x x )			
Concomitant medications	x y		To be recorded continually until end of treatment y													
Adverse events z	x		To be assessed continually z													
PET-CT scan	x aa											x bb		x jj		
CT scan cc	x cc											x bb	At end of Month 3	x ee	x ff	
Bone marrow biopsy and aspirate	x gg											x bb, hh	x hh	x ee, hh		
Study treatment administration	Rituximab ii			x				x						x		
	Polatuzumab vedotin ii			x				x								
	Lenalidomide ii			D1-21				D1-21					D1-21			
New anti-lymphoma treatment															x	x
Survival follow-up																x

ATA = anti-therapeutic antibody; CT = computed tomography; D = day; ECOG = Eastern Cooperative Oncology Group; eCRF = electronic Case Report Form; EOC = end of consolidation; EOI = end of induction; FU = follow-up; HAHA = human anti-human antibody; IPI = International Prognostic Index; MRD = minimal residual disease; MRI = magnetic resonance imaging; PET = positron emission tomography; PK = pharmacokinetic; Q3M = every 3 months; RCR = Roche Clinical Repository; wk = week.

## Appendix 2

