### Schedule of Assessments for Patients with Diffuse Large B-Cell Lymphoma (cont.)

---

- z After informed consent has been obtained but prior to initiation of study treatment, only serious adverse events caused by a protocol-mandated intervention should be reported. After initiation of study treatment, all adverse events will be reported until 90 days after the last dose of study treatment. After this period, the Sponsor should be notified if the investigator becomes aware of any serious adverse event that is believed to be related to prior study treatment (see Section 5.6). The investigator should follow each adverse event until the event has resolved to baseline grade or better, the event is assessed as stable by the investigator, the patient is lost to follow-up, or the patient withdraws consent. Every effort should be made to follow all serious adverse events considered to be related to any of the study treatment components or trial-related procedures until a final outcome can be reported.
- aa The screening PET-CT scan must be performed within 35 days prior to Day 1 of Cycle 1.
- bb Perform only for patients who have received at least two cycles of induction treatment.
- cc Includes CT scan of the neck (if clinically indicated), chest, abdomen, and pelvis. If contrast is medically contraindicated (e.g., patients with contrast allergy or impaired renal clearance), MRI scans of the chest, abdomen, and pelvis (and neck, if clinically indicated) and a non-contrast CT scan of the chest may be performed. Combined PET/CT scanners may be used to collect diagnostic CT scans, but only according to the technical guidelines in the imaging manual. The screening CT scan must be performed within 35 days prior to Day 1 of Cycle 1.
- dd Perform within 7 days prior to Day 1 of Cycle 3.
- ee Perform only if not done within the previous 3 months.
- ff Perform every 6 months.
- gg Bone marrow biopsy and aspirate must be performed within approximately 3 months prior to Day 1 of Cycle 1.

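### The 6-month PFS/EFS landmark falls before nearly every end-of-induction scan, so the reported event-free rate is biased upward; the later landmarks are affected only in part

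*Combined protocol and SAP*

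**What the plan says.** Section 6.6.3 summarizes PFS, EFS, DFS and OS by Kaplan-Meier and adds landmark rates: the proportion "event free at 6 months, 9 months, 1 year, and 2 years will be provided". For PFS, EFS and DFS, "data for patients without an event of interest will be censored at the date of the last tumor assessment". There is no interval-censoring, no visit-window rule, and no statement of whether a landmark month is a calendar month or the 28-day month defined for treatment in the notes to Figure 1.

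Section 2.2.3 gives the origin and event: "PFS, defined as the time from initiation of study treatment to first occurrence of disease progression or relapse, as determined by investigator". The synopsis adds the imaging modality ("as determined by investigator on the basis of CT scans alone, or death from any cause"); Section 2.2.3 does not.

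The scan calendar comes from Section 4.3.2 and Appendices 1 and 2:

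- Patients "will receive six 28-day cycles of induction treatment".
- Interim CT, both histologies: "Perform within 7 days prior to Day 1 of Cycle 3".
- EOI, both histologies: "EOI assessments should be performed 6–8 weeks after Day 1 of the last induction cycle".
- FL after EOI: CT at 12, 18 and 24 months from the start of induction.
- DLBCL in consolidation: CT "At end of Month 3", then at end of consolidation (EOC), 35 days after the last dose.

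Section 4.5.5.1 requires a full tumor assessment, with imaging, whenever progression or relapse is suspected.

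**The concern.** Under the plan a progression that causes no suspicion is dated when a scan finds it. A landmark that falls late in a gap between scans, shortly before the scan that closes the gap, reads the curve before its step. Patients who have already progressed but have not been scanned count as event free, so the error is always upward.

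This is a single-arm trial, and its PFS rates will naturally be read beside outside results obtained on other scan schedules. A favorable 6-month rate could then reflect visit timing as much as disease control. DFS is left out of the check because its clock starts at first documented CR, so the calendar from treatment start does not carry over to it.

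**Working it through.** **Calendar (Cycle 1 Day 1 = day 0; calendar month = 30.44 days)**

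The plan's own figure first. Cycle 6 Day 1 = 5 × 28 = day 140. Consolidation starts 8 weeks later, at day 196 (±7). Six 28-day months end at 196 + 168 = day 364, or 11.96 months. That reproduces the total DLBCL treatment duration of about 12 months in Section 3.3.3.4.

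Scans on the same calendar:

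- Interim CT: Cycle 3 Day 1 = day 56, so day 49–56.
- EOI: 140 + 42 to 140 + 56 = day 182–196.
- DLBCL Month 3 CT: 196 + 84 = day 280 (273–287).
- DLBCL EOC: if the last dose is lenalidomide on Day 21 of Month 6, 196 + 160 + 35 = day 391 (384–398).

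| Landmark | Day (28-day months) | FL | DLBCL |
|---|---|---|---|
| 6 months | 182.6 (168) | before almost all of the EOI window | same |
| 9 months | 273.9 (252) | no scan between EOI and 12 months | about 6 days before the Month 3 CT (consolidation only) |
| 12 months | 365.25 (336) | scan nominally on the day | about 26 days before the EOC CT (consolidation completed) |
| 24 months | 730.5 (672) | scan nominally on the day | consolidation scans are over |

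With 28-day months the 6-month landmark precedes every on-schedule EOI scan. Treatment delays move EOI, and the DLBCL scans after it, further past the landmarks.

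**Size of the bias**

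Assumptions: exponential progression times, S(t) = 0.5^(t/median), with scans spread evenly over their windows. Medians are from Section 1.3.2.1: 5.6 months (DLBCL, rituximab plus polatuzumab vedotin 2.4 mg/kg, n = 39) and 18.1 months (FL, same doublet at 1.8 mg/kg, n = 20). A share q of progressions is found at onset through unscheduled assessment; the rest wait for the next scheduled scan. Simulated results, calendar months:

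| | True | Reported, q = 0 | Reported, q = 50% |
|---|---|---|---|
| DLBCL 6 months | 47.5% | 79.3% | 63.5% |
| DLBCL 9 months | 32.8% | 45.4% | 39.2% |
| DLBCL 12 months | 22.6% | 32.0% | 27.4% |
| FL 6 months | 79.4% | 93.0% | 86.3% |
| FL 9 months | 70.8% | 78.8% | 74.8% |

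At q = 75%, DLBCL at 6 months is 47.5 + 0.25 × (79.3 − 47.5) = 55%. A hand check of the top value: the interim CT at day 56 is 1.84 months, and 0.5^(1.84/5.6) = 80%, close to the simulated 79%.

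The DLBCL 9- and 12-month rows put every patient on the consolidation calendar. For FL at 12 months, an assumed ±7-day scan window, which leaves half the scans late, gives 63.1% true against 71.1% reported at q = 0.

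**Reading just after the windows close** (same model, q = 0, true vs reported)

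- DLBCL: day 197, 44.8% vs 46.3%; day 288, 30.9% vs 31.9%; day 399, 19.7% vs 20.4%.
- FL: day 197, 78.1% vs 78.9%; day 373, 62.6% vs 63.2%; day 738, 39.5% vs 39.9%.

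The residual bias is 0.4 to 1.5 points. Leaving more room for delays costs a little. At 7 months it is S(189 days) − S(7 months): 46.4 − 42.0 = about 4 points in DLBCL and 78.8 − 76.5 = about 2 points in FL.

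**The case against.** A reader might infer that every landmark in both histologies sits just before a scan, so that all the long-term rates are inflated in the same way. The documents do not support that. FL has no scan near 9 months; the inflation there comes from the gap between EOI and 12 months. At 12 and 24 months the FL scan is due on the landmark itself, and Kaplan-Meier at time t already includes events dated at t, so on-time findings are counted. The 12-month PET-CT for patients PET-positive at EOI is done within the 14 days before dosing and may fall earlier still. In DLBCL the Month 3 and EOC scans apply only to patients with CR or PR who enter consolidation; the others go to follow-up with CT every 6 months. If the last dose were the Month 5 rituximab infusion, EOC would fall at 196 + 112 + 35 = day 343, before 12 months.

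A reader might also take the largest figures as forecasts. They need every progression to stay unsuspected until the scan. Section 4.5.5.1 requires imaging on suspicion, targeted examinations cover nodes, liver and spleen, and deaths (and, for EFS, new therapy) are dated independently of scans. In relapsed or refractory DLBCL the zero-detection end is implausible. The 5.6-month median comes from a polatuzumab vedotin dose the sponsor no longer pursues (Section 1.3.2.2). Both medians are themselves observed trial PFS, so the true rates are true only within the model.

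Nor are these the only long-term figures. Section 6.6.3 also gives full curves, medians, and CR at 12 months or EOC in patients PET-positive at EOI. The endpoints are exploratory, with no test or decision attached.

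All of this stands. It limits the later landmarks and the size, but it does not remove the 6-month problem, which arises from the schedule in both histologies.

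**Conclusion.** The concern holds for the 6-month PFS and EFS rates in both histologies, and at 9 and 12 months for DLBCL patients in consolidation (at 12 months, if the last dose is Month 6 lenalidomide). For FL, the 9-month rate is inflated by the scan gap, and the 12- and 24-month rates only to the extent that scans run late.

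The direction is upward throughout. The size depends on how many progressions are found between scans, which the documents do not give. At 6 months the illustrative excess in DLBCL runs from about 32 points (none found early) to 8 (three quarters found), and in FL it is about 14 points (none) or 7 (half). These rest on exponential times, medians borrowed from doublet studies, calendar months and no treatment delay.

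Because the endpoints are exploratory and descriptive, this is an inexpensive improvement rather than a defect that threatens the trial's conclusions. The imaging-modality mismatch between the synopsis and Section 2.2.3 is a separate wording point and lends no support to the landmark finding.

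**What to change.** In Section 6.6.3, for PFS and EFS, do one of the following:

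- Add histology-specific landmarks just after each scan window closes: about 7 months for both; about 10 and 13.5 months for DLBCL; about 12.5–13 and 24.5–25 months for FL. Rely on no FL landmark at 9–10 months.
- Or add an interval-censored (Turnbull) estimate at the planned times.

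One shared list of later times would not serve. In FL at 10 months there has still been no scan since EOI, and the illustrative bias at q = 0 rises to S(189 days) − S(10 months) = 78.8 − 68.2 = about 11 points, against 8 at 9 months.

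Keep 6, 9, 12 and 24 months for OS and as supportive figures for PFS and EFS. State which month definition the landmarks use. Separately, align Section 2.2.3 with the synopsis on whether PFS, EFS and DFS rest on CT alone.

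The cost is SAP wording and some programming, with no change to visits or data collection. The downside is less conventional time points, which keeping the planned ones as supportive largely offsets.
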